| Screening & Consent | x | | | | | | | |
| Tanner staging | x | | | | | | | |
| ¹³C gastric emptying breath test | | x | | | | | | |
| Satiety Drink Test | | | x | | | | | |
| Heart Rate Variability | x | | | x ¹ | | x ¹ | | |
| Nausea Profile | x | | | x | x | x | x | x |
| BARF scale | x | | | x | x | x | x | x |
| SUDS scale | x | | | x | x | x | x | x |

| | | | | | | | | |
|---|---|--|--|---|---|---|---|---|
| API (pain and nausea) | x | | | x | x | x | x | x |
| PROMIS anxiety & global health | x | | | x | x | x | x | x |
| FDI | x | | | x | x | x | x | x |
| Nausea Severity Scale | x | | | x | x | x | x | x |
| CSI | x | | | x | x | x | x | x |
| VSI | x | | | x | x | x | x | x |
| PAGI-SYM | x | | | x | x | x | x | x |
| ROME IV | x | | | | | | | |
| Symptom response scale | | | | | x | x | x | x |
| Neurostimulator (active or sham) | | | | x | x | x | | |
| fMRI scan (subset) | | | | x | | | x | |

NP=Nausea Profile; API=Abdominal Pain Index; PROMIS= Patient Reported Outcome Measurement Information System; FDI=Functional Disability Inventory; CSI=Children's Somatization Inventory; VSI=Visceral Sensitivity Index; PAGI-SYM=Patient Assessment of Upper Gastrointestinal Symptom Severity Index

x¹ HRV will be completed prior to and after neurostimulator placement.

All procedures will be performed in the Children's Hospital of Wisconsin (CHW) Pediatric Translational Research Unit (pTRU). Prepackaged kits (Cairn Diagnostics, Brentwood, TN, USA) for the gastric emptying breath test and nutrient drinks will be stored by research coordinators in locked offices within the Division of Gastroenterology and brought to the pTRU on the day of testing. The prepackaged kits for the gastric emptying test and neurostimulators will be shipped by manufacturer when requested by PI. A box labeled with subject ID and containing neurostimulators (four), a GEBT kit and a labeled folder with patient ID and relevant questionnaires will be premade and kept with each subject package. After the breath test is performed, research coordinators will ship the samples to Cairn Diagnostics within 2 days of collection.

Measurements and Data Collection

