1. Nausea Profile (NP). The NP is a two page, 17-item questionnaire validated in adolescents which measures the subjective experience of nausea on a scale from 0 (not at all) to 9 (severely) across three dimensions: 1) somatic distress; 2) GI distress and 3) emotional distress.⁸⁷ The subjects will be asked to rate their nausea over the past week. Three subscale scores and a total score is generated which can be used to measure an individual's experience of nausea and how it changes over time.⁸⁸ This instrument has demonstrated

excellent internal reliability in adolescents (Cronbach's $\alpha=0.941$).³² Subjects will also rate their usual level of nausea on a scale from 0 to 10 (10 being the worst nausea imaginable).

2. Baxter Retching Faces (BARF): pictorial daily nausea severity rating scale (0-10)⁸³
3. Subjective Unit of Distress Scale (SUDS): during active treatment (3x) and off days (1x) to measure amount of distress on a severity scale (0=peace to 10=nervous breakdown)⁸⁹ (weekly averages will be computed)
4. Abdominal Pain Index (API). The API is a short, one-page instrument validated in children with functional abdominal pain.⁹⁰ A revised form of this scale will be used to assess nausea (=Nausea Severity Scale).
5. Patient Reported Outcomes Measurement Systems (PROMIS) Pediatric Anxiety-Short Form scale:⁹¹ Symptoms of anxiety will be assessed via the short, 8-item PROMIS anxiety short form. A Research Psychologist (PhD) will assist with interpretation of the psychometric data. Scores will be compared against healthy norms, and pediatric chronic pain patients.
6. Patient Reported Outcome Measurement Information System (PROMIS) Global healthy: A newly developed and validated global health/quality of life outcome measure that provides an efficient (7-item) summary of a child's physical, mental and social health (both self and parental reports will be assessed).⁹²
7. Functional Disability Inventory (FDI): Symptoms of disability and reduced quality of life secondary to pain nausea will be assessed with the FDI child and parent report forms.⁹³ This is a one page, self-report measure of the degree that children experience difficulty in physical and psychosocial functioning due to impaired physical health. Patients and parents rate each of the 15-items on a five-point Likert scale indicating how much difficulty they have doing common childhood activities because of their physical health.

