Involved risks are minimal. Possible risks involve allergies to contents of formula or premade meal for GEBT; although these will be carefully screened for prior to enrollment there is a possibility of unknown allergies. Patients may experience some discomfort, nausea and possible vomiting with satiety drink test. However, patients are instructed to cease drinking at point of satiety so extreme symptoms should not be experienced.

Questionnaires:

Patient distress during questionnaire completion: If children become distressed during completion of study questionnaires, they are instructed in the consent and assent forms to inform the researchers or nurse. The researchers/nurse will then contact the primary investigator who will place a referral to a psychologist as necessary and as dictated by law (e.g., suspected child abuse/neglect) to ensure patient and family safety and to address psychosocial needs.

Patient/Parent report of clinically significant psychosocial or safety issues: Any child endorsing clinically significant psychological distress on questionnaire-reported screening measures will be referred to a psychologist. The PROMIS anxiety and global health scales will be scored by research coordinators within a week of completion. The raw score will be converted to a standardized T score where a T score of 50 represents the mean for a U.S. general pediatric population with a standard deviation of 10. Subjects scoring greater than 2 standard deviations below the mean will be reported to the PI. The PI will discuss the results with the family and provide them with a referral to a licensed clinical psychologist ([name]) as necessary.

Heart Rate Variability:

Participants will be asked in advance if they have a history of skin allergy to adhesives to avoid provoking any skin irritation or rash. However, some redness from the adhesive on the ECG surface electrodes may temporarily appear.

Neurostimulation:

Overall risks/ discomforts involved are very minimal – Rare (event rate 1% - < 5%)

Possible risks/discomforts may involve:

- a. Discomfort upon insertion of the electrodes for < 5 minutes - Rare (event rate 1% - < 5%)
- b. Discomfort at the lead placement site > 5 minutes – Rare (1 % - < 5%)
- c. Bleeding at the electrode site if the neurovascular bundle is penetrated - Rare (event rate 1% - < 5%)
- d. Localized discomfort if the electrodes should become dislodged during the wearing of the device - Rare (event rate 1% - < 5%)

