Patient/Parent report of clinically significant psychosocial or safety issues: Any child endorsing clinically significant psychological distress on questionnaire-reported screening measures will be referred to a psychologist. Regarding psychological screeners, research assistants will score the PROMIS questionnaires within a week of completion. Any scores 2 or more standard deviations above mean will be reported to the PI. In turn, the PI will discuss the results with the family and provide them with a referral to a licensed clinical psychologist as necessary.

I. PROVISION FOR THE PROTECTION OF PRIVACY OF SUBJECTS AND TO MAINTAIN THE CONFIDENTIALITY OF DATA

All research projects that collect electronic data must use appropriate security measures to ensure that data is protected from theft or loss in order to prevent breaches of confidentiality. You must indicate what encryption tools (or why they are not necessary) from the options below. The IRB will not review this protocol unless you indicate the encryption tools being used to secure your research data. If you do not have encryption in place on your systems, please contact your Information Systems support to arrange for one of the encryptions options listed below.

The following encryption products employ cryptographic modules that the National Institute of Standards and Technology has certified as meeting FIPS 140-2 requirements. Children's Hospital and Health System endorsed the use of these products made to encrypt hard drives and removable media. All electronic research data must be encrypted using one or more of these products.

Please indicate which encryption tools you are using to secure your research data.

- Credent Mobile Guardian (RS, PD)
- GuardianEdge Hard Disk and GuardianEdge Removable Storage Encryption (HD, RS, PD)
- IronKey encrypted flash drives (RS)
- McAfee Endpoint Encryption (HD, RS)
- Microsoft Bitlocker (HD, RS when used with Windows 7 and FIPS compliant algorithms are enabled)
- PGP Whole Disk Encryption and PGP Portable (HD, RS)
- SafeNet Protect Disk and SafeNet Protect File (HD, RS)
- Seagate Secure Self-Encrypting Drives (HD when encryption option is enabled)
- Symantec Endpoint Encryption (HD, RS, PD)
- WinMagic SecureDoc encryption (HD) (for MCW owned computers)
- Other (add description)

Does not apply because:

- Data is de-identified – no PHI collected
- Data is stored on paper only
- Data is stored on CHW secured shared drives.

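### The two PROMIS cut-offs for reporting a child to the PI point in opposite directions, and neither is set per scale

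*Combined protocol and SAP*

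**What the plan says.** Section H states the same safety step in two places.

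- **Questionnaires subsection.** "The PROMIS anxiety and global health scales will be scored by research coordinators within a week of completion". Raw scores become T scores with a general pediatric mean of 50 and SD of 10. Then: "Subjects scoring greater than 2 standard deviations below the mean will be reported to the PI". Both scales fall under this one rule.
- **Safety Analysis Plan.** "research assistants will score the PROMIS questionnaires within a week of completion". Then: "Any scores 2 or more standard deviations above mean will be reported to the PI". The scales are not separated here either.

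In both places a report leads to the PI discussing the result with the family and referring to a psychologist as needed. Both also open with a general rule that has no threshold: "Any child endorsing clinically significant psychological distress on questionnaire-reported screening measures will be referred to a psychologist".

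The instrument list in Section F (Questionnaires, items 5 and 6) describes the two scales. For the first: "Symptoms of anxiety will be assessed via the short, 8-item PROMIS anxiety short form". The second is a seven-item summary of the child's health and quality of life, with child and parent versions. Neither item gives a scoring direction or a cut-off.

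**The concern.** The two statements cover the same scoring, the same recipient and the same follow-up, but they use opposite tails of the distribution. They also differ at the boundary (more than 2 SD against 2 SD or more) and in who does the scoring, which are smaller matters.

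An anxiety scale and a health scale would ordinarily have their worst scores at opposite ends, so no rule confined to one tail can serve both. A staff member who works from only one of the two texts will miss the worst scores on one scale.

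At stake is the detection and referral of distressed minors. The Safety Analysis Plan itself notes that the questionnaires may bring out symptoms that neither patient nor parent knew of. Specific Aim 1 hypothesises high anxiety in functional nausea, so the upper anxiety tail is the one the protocol has reason to expect children in.

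**Working it through.** **The two rules on the T scale** (mean 50, SD 10, from Section H, Questionnaires)

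- Questionnaires rule: T < 50 − 2 × 10 = 30.
- Safety Analysis Plan rule: T ≥ 50 + 2 × 10 = 70.

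No single score can meet both.

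**What needs no assumption.** On any one scale, bad scores are either high or low. If high, the Questionnaires rule used alone reports the well tail; if low, the Safety Analysis Plan rule does. So for each scale one of the two texts is wrong as written.

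**Which text fails for which scale.** This needs a scoring direction, which the documents do not give. Assume that a higher T means more anxiety on one scale and better health on the other:

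| Rule followed alone | Anxiety | Global health |
|---|---|---|
| T < 30 | reports the least anxious, misses the most anxious | reports the poorest health (correct) |
| T ≥ 70 | reports the most anxious (correct) | reports the best health, misses the poorest |

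**Illustrative size.** The documents give no PROMIS distribution for this population. Take scores as normal with SD 10, a sample mean μ equal to the norm or shifted in the bad direction, and the planned 80-100 adolescents with chronic nausea. For anxiety:

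- worst tail: P(T ≥ 70) = 1 − Φ((70 − μ)/10)
- wrong tail: P(T < 30) = Φ((30 − μ)/10)

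| Assumed mean anxiety T | P(T ≥ 70) | Children of 80-100 | P(T < 30) | Children of 80-100 |
|---|---|---|---|---|
| 50 (the norm) | 0.0228 | 1.8-2.3 | 0.0228 | 1.8-2.3 |
| 55 (0.5 SD worse) | 0.0668 | 5.3-6.7 | 0.0062 | 0.5-0.6 |
| 60 (1 SD worse) | 0.1587 | 12.7-15.9 | 0.0013 | 0.1 |

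Global health is the mirror image, with means of 50, 45 and 40 and the tails exchanged. The figures are per scale and per assessment.

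**How often the rule is applied.** In Table 1 (Section F) the row "PROMIS anxiety & global health" is marked at Pre, Visit 3, Visits 4-5, Visit 6, Post #1 and Post #2: 1 + 1 + 2 + 1 + 1 + 1 = 7 assessments. Children who enter the second four-week course add Visits 7-10 and Posts #3 and #4, so 7 + 6 = 13 if the same questionnaires are given at each. The base of 80-100 does not count the IBS patients separately.

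**The case against.** The strongest reply is that the two sentences do not exclude each other. Neither says only. Staff who obey the whole document would report T < 30 and T ≥ 70 and, under the scoring assumption above, would catch the worst tail of both scales apart from a global health score of exactly 30. The price is some needless reports of well children. Logically this is right: children are missed only if one text is followed alone. But nothing tells staff to combine the rules, each text reads as complete, and the two name different scorers.

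The second reply is that the numeric cut-off is not the only route to referral. Both places refer any child who endorses clinically significant distress, distress during completion goes to the PI, and a research psychologist helps interpret the psychometric data. These safeguards are real and lower the risk. None supplies a threshold, however, and the PROMIS rule is the only numeric one. The PI's judgement on whether referral is needed comes into play only after a report.

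Third, the harm depends on a scoring direction the documents do not give, and the mean shifts are assumed. That limits what can be said about which rule fails for which scale and how many children are affected. It does not touch the contradiction itself.

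Finally, no endpoint, sample size or eligibility criterion is involved, and poor global health is not necessarily psychological distress. Both points stand. They keep this a correction to the safety text.

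**Conclusion.** The concern holds. One safety decision is given two opposite thresholds, T below 30 and T of 70 or more, and neither is assigned to a scale. That conclusion rests on the text alone.

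That the Questionnaires rule alone misses the most anxious children, and the Safety Analysis Plan rule alone misses the poorest global health, rests on the assumption that higher T means more of the named construct. The counts of about 2, 5-7 or 13-16 children per scale at one assessment rest further on normal scores with SD 10 and assumed mean shifts of 0, 0.5 and 1 SD; they show scale and are not a forecast for this trial. The efficacy analysis is unaffected. The text should be corrected because it governs referral of minors and the remedy is simple.

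**What to change.** Put the same sentence in both places in Section H, for example:

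> A PROMIS anxiety T score of 70 or higher (at least 2 SD above the mean), or a PROMIS global health T score of 30 or lower (at least 2 SD below the mean), triggers a report to the PI.

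Before adopting it, have the study psychologist confirm the scoring direction of each scale. Name the same scorer in both places, and say whether a parent-reported global health score also triggers a report. The lower boundary now includes a score of exactly 30, which the Questionnaires rule leaves out.

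The cost is one sentence in two subsections. No new data are needed, because the scales are already scored within a week. Reports to the PI may rise; the number depends on how far this population sits from the norm, as in the illustration above, and those added are the children the rule is meant to find.

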Subjects will enter a 4-week, prospective randomized, double blind sham controlled treatment trial with the FDA-approved and commercially available EAD manufactured by Key Electronics (Jeffersonville, IN, USA) and distributed by Innovative Health Solutions (Versailles, IN, USA). The device is cleared under the BWK classification, with intended use in the practice of acupuncture by qualified practitioners of acupuncture as determined by the states. EAD is an ambulatory, neurological device which consists of a battery powered, externally affixed generator with 4 wire leads attached to 3 electrode/ needle arrays and one single point needle. The arrays are designed to produce a field effect similar to surgically implanted peripheral neurostimulators. The electrodes will be placed percutaneously in the external ear with the help of a transilluminator to visualize the neurovascular bundles. Three electrodes will be placed on the ventral and one on the dorsal aspect of the ear. The electrodes will be taped and secured behind the ear next to the generator itself which is secured to the skin with adhesive. The entire device may be covered by longer hair. The placement of the devices is within standard of care by properly trained medical doctors as already completed trial at CHW (IRB# 689519-17). Training of MDs has been performed by [name] or [name] as representatives of Innovative Health Solutions. Training of other involved physicians may be performed if protocol approved. 40-50 subjects will receive the active EAD device while 40-50 subjects will receive an inactive device that is identical to the active device but lacking the battery.

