Subjects will be randomized in a 1:1 ratio to either treatment or sham group. Randomization will be determined using a computer program based on random number generation in blocks of 10 subjects at a time. The manufacturer will provide the researchers with four devices per package (4 weeks per patient) and distribute 10 packages at a time to the investigators. Each package will have a serial number and only one research coordinator will have the key to which serial numbers represent active devices and which represent inactive ones. This research coordinator will keep the data in a secure database and will not be involved in any of the patient recruitment or study procedures. All other research coordinators, investigators, statistician and nurses involved will be blinded. Research coordinators within the division of gastroenterology will store the devices as pre-packaged by manufacturer and label the devices with a serial number and patient ID number. A labeled folder for each patient with all questionnaires needed for the entire study will also be kept with each subject package. The devices and folders will be stored in a locked office in the gastroenterology division, only accessible by research coordinators. Password protected iPads will be used to collect questionnaire information from participants. No PHI will be loaded on these iPads.

A blinded research coordinator will bring each subject's numbered package to the research area (Translational Research Unit) when patient arrives. The package for the subject will be stored locked in the TRU until the subject finishes the 4 week therapy. The coordinator will ask the subject to complete the pre-placement questionnaires (Table 1; visit #3) and hand the device (numbered with serial # and patient ID only) to one of the certified MDs for placement. The devices will be "made to order" when requested by the PI and will be shipped packaged as above.

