Patients will be told that they may or may not feel a slight flushing or tingling sensation after device placement. The electrode/needle arrays are implanted according to the individual's arterial and cranial nerve anatomy. The exact location of the implantation may vary slightly from person to person but is determined by both knowledge of auricular neuro-anatomy and visualization of the neurovascular bundles by trans-illumination (IHS, Versailles, IN, USA). The points will be targeted by four-point electrical stimulation using the EAD device after carefully disinfecting the ear. The small device will be positioned and secured behind the ear similar to a hearing aid, which may be covered by hair. Neurostimulation will be delivered below sensation threshold continuously for 5 consecutive days. The EAD device will be applied by a trained MD. Subjects will remove the device independently at home and discard them as they are non-functioning after 5 days (5 days battery life). If a device is lost or broken, the research team will attempt to schedule placement of a new EAD within 1 day if you wish. The devices are easily removed by removing the tapes and adhesives. Before and during the treatment trial, subjects and parents will complete questionnaires as shown in Table 1.

The EAD Surgical kit consists of :

- an alcohol swab
- prep and stay swab
- round fixation plasters
- fixation plasters to fasten the generator
- Steri-strip adhesive vial
- Sterile wire harness pack
- Generator
- Tweezers
- Surgical marker
- Transilluminator

EAD placement details:

1. A research coordinator in the GI office will be asked to open the package and obtain either a true device or a control device as outlined in a randomization scheme provided by the statistician. This research coordinator will document the patient ID, name and the device serial number in the study database and whether assigned to an active vs inactive device. This lead research coordinator will be the only unblinded person and she will not be involved in any patient contact or other parts of the study.

2. The neurostimulator placement will be performed as directed and per EAD training protocol instructions identically to prior CHW IRB approved trial.

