3. Before neurostimulator placement, the subject should be advised that some discomfort is normal at first but should report if the discomfort persists or gets worse after a few minutes. The patients should be advised that they may feel a slight pulsing sensation and perhaps a warming sensation in the ear to which the electrodes are affixed. The pulsing and warming sensation may disappear after approximately 5 minutes. If the discomfort level increases the offending electrode can be slightly repositioned until the patient's discomfort level decreases to an acceptable level.
4. Device placement will take approximately 5 minutes. The patient will remain at rest for the next 5 minutes.
5. The subject will be advised not to immerse the device in water as the device is water resistant but not water proof. If showering or washing their hair, subjects will be instructed to place a dry wash cloth or plastic such as Press n' seal over the area to help protect the device. Subjects will be given a contact person (primary investigator and research coordinator) to call if they are having any problems with the device or if it falls off.
6. The patient will be instructed on removing the device after 5 days. If not comfortable doing so or unable to carry out the instructions, the patient may be seen that day for removal by one of the investigators.
7. At the end of the study (post-neurostimulation #1), subjects will be asked to guess their group allocation to test blinding.
8. The patient will be asked to return the used device for proper disposal when they return for their follow-up appointment.
9. The subject will be given a handout with information (attached) on device handling, exact date and time of device removal and date and time to return.
10. The subject will be advised to refrain from using any new or as needed anti-emetic or pain medications.
11. The subject is dismissed.

Optional fMRI sub-study

Participants will be given the option to participate in the fMRI sub-study. Post menarche patients must yield a negative urine pregnancy test on the day of each scan. Participants will then be escorted to the fMRI scanner in the lower level of FH where they will complete the safety screening questionnaire. The patient will be given the option of lying down in the mock scanner prior to their first fMRI scan.

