- Data is stored on MCW secured shared drives.

Key

HD = Hard Drive

RS = Removable Storage (USB flash drive, CD, etc.)

PD = Portable Device (iPod; iPhone; PDA, etc.)

Each subject will be assigned a unique identifying number which will be the only identifier listed on the questionnaires, GEBT and neurostimulator kits and all data collection forms. Each subject's identifying number and related electronic data will be kept on a secured, MCW password-protected database that provides access only to the PI and research staff. Only authorized research personnel will have access to the database. A separate secure database will have the subject identification number linked to the patient's name and info. The GEBT kits and neurostimulator devices will be shipped directly from the manufacturer (Key Electronics) to the GI office research coordinator who will label each package of 4 neurostimulator devices with a patient ID and serial number with a prepared sticker label. A subject folder will also be prepared and labeled with the same ID and kept together with the device package. The devices will be stored in a locked room in the division of gastroenterology. The kits will be transported by a research coordinator to the TRU on the day needed. The remaining kits will be stored in a locked room in the GI clinic, labeled with the patient's ID. Only research coordinators within the division of gastroenterology will have access to the storage room. To track use and

proper disposal of the devices, subjects will be asked to return the used device the following week (at time of the next stimulator placement or follow-up clinic visit if week 4). The doctor or research coordinator will record that device was returned and dispose it properly. The research coordinator will log this data every week on each subject as devices are returned.

J. PROVISIONS FOR MONITORING DATA TO ENSURE THE SAFETY OF SUBJECTS; AND ADDITIONAL SAFEGUARDS TO PROTECT THE RIGHTS AND WELFARE OF SUBJECTS WHO ARE LIKELY TO BE VULNERABLE

The PI will monitor the health of all patients in the study per standard clinical practice. The PI will monitor protocol adherence and supervise data collection, entry, and analysis.

K. ANTICIPATED BENEFITS ASSOCIATED WITH THE PROTOCOL TO HUMAN RESEARCH PARTICIPANTS AND SOCIETY

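### Blinding is at risk, though not shown to fail: the sham lacks a battery, used devices go back to staff who should be blinded, and the return and sensation instructions do not agree

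*Combined protocol and SAP*

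**What the plan says.** - **Sham.** Section F, Auricular Neurostimulation (EAD) treatment protocol: "40-50 subjects will receive an inactive device that is identical to the active device but lacking the battery". The generator is battery powered. Nothing is said about whether the battery space is sealed, opaque or matched for weight.
- **Who is blinded.** The same section names one coordinator who holds the key, then states: "All other research coordinators, investigators, statistician and nurses involved will be blinded". Step 1 of EAD placement details adds that this coordinator has no patient contact.
- **Used devices.** Section F: "Subjects will remove the device independently at home and discard them as they are non-functioning after 5 days". Section I instead has subjects return each device at the next placement, or at the clinic follow-up visit for the week 4 device, and continues: "The doctor or research coordinator will record that device was returned and dispose it properly". Step 8 of EAD placement details also asks for return, at the follow-up appointment.
- **Sensation.** Section F: "Neurostimulation will be delivered below sensation threshold continuously for 5 consecutive days". In the same paragraph, subjects are told that flushing or tingling might or might not occur. Step 3 of EAD placement details has them told that "they may feel a slight pulsing sensation and perhaps a warming sensation in the ear to which the electrodes are affixed", and that this can fade after roughly 5 minutes.
- **Check on blinding.** Step 7: subjects guess their arm once, at post-neurostimulation #1.
- **Primary outcome.** Power section, Aim 3: the Nausea Severity Scale total score after 4 weeks, which subjects complete themselves.
- **Randomization.** 1:1, "based on random number generation in blocks of 10 subjects at a time", with packages delivered ten at a time.

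**The concern.** The only stated physical difference between the arms is inside an object that subjects wear, remove and, under Section I, hand to staff who are meant to be blinded. If the missing battery can be noticed, the return step puts it in front of those staff each week while the blinded outcome is still being collected. A second possible cue is sensation. A device without a battery delivers no electrical pulse, and one of the two scripts draws attention to pulsing.

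The primary outcome and most secondary outcomes are questionnaires. A subject who works out the arm, or a doctor who does and conveys it, could shift the active-sham difference through expectation. The planned guess could show afterwards that this happened but would not prevent it, and staff are not asked to guess.

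**Working it through.** The plan gives no figure for blinding success, so there is none to reproduce. The check compares the passages and then sizes the possible consequences.

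**1. When used devices reach staff.** Devices are placed at Visits 3, 4, 5 and 6 (Section D, Protocol and Procedures). Under Section I, device 1 returns at Visit 4, device 2 at Visit 5 and device 3 at Visit 6. Device 4 returns at the clinic follow-up, after the week 4 assessment. So 3 of 4 devices (3/4 = 75%) are returned before the primary assessment. Staff first see one about a week after the first placement.

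**2. Who receives them.** Section I names the doctor or a research coordinator. The unblinded coordinator has no patient contact, so as written whoever takes the device at a placement visit is someone meant to be blinded. No closed container is mentioned.

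**3. Discard or return.** The Section F discard instruction and the Section I return instruction cannot both be followed. Step 8 is compatible with Section I for the week 4 device. The contradiction is therefore discard against return.

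**4. Sensation.** Both scripts are conditional, and neither is said to differ by arm. Step 3 mentions pulsing and warming; the earlier paragraph mentions flushing or tingling. Possible pulsing also sits awkwardly with sub-threshold delivery.

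**5. Predictability of later assignments, if earlier arms were identified.** Exact 5:5 balance per block is implied by 1:1 in blocks of 10, not written out. With m = 5 per arm, and a guesser who always names the arm that is behind, expected correct guesses per block are m + 2^(2m-1)/C(2m,m) - 1/2 = 5 + 512/252 - 0.5 = 6.53 of 10. Enumerating all C(10,5) = 252 blocks gives the same value, and shows the effect of a lag:

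| Most recent assignments still unknown | Correct guesses of 10 | Certain assignments of 10 |
|---|---|---|
| 0 | 6.53 | 1.67 |
| 1 | 6.03 | 0.67 |
| 2 | 5.81 | 0.22 |
| 4 | 5.44 | 0.01 |

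Chance is 5.0. If only half of the earlier arms are identified (an assumption), simulation gives 5.68 with no lag and 5.45 with the last two unknown. The enrolment rate is not given, so the lag is also an assumption.

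**6. Illustration of bias in the primary outcome.** The Power section gives about 40 per group and 12% dropout: 40 × 0.88 = 35.2, matching its figure of about 35, read here as per group. Assume no true effect, an unblinded share u, and an expectation difference e (in SD) between unblinded active and unblinded sham subjects. The bias is d = u × e. With u = 25% to 50% and e = 0.2 to 0.4, d runs from 0.25 × 0.2 = 0.05 to 0.50 × 0.4 = 0.20 SD. None of these inputs is in the documents.

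The false-positive rate is Φ(-1.96 + z) + Φ(-1.96 - z), with z = d/√(2/35) = d/0.239:

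| d (SD) | z | False-positive rate |
|---|---|---|
| 0 | 0 | 5.0% |
| 0.05 | 0.21 | 5.5% |
| 0.10 | 0.42 | 7.0% |
| 0.20 | 0.84 | 13.3% |

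If the blind holds, d = 0 and nothing is lost.

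**The case against.** **The blind may well hold.** A reader might infer that allocation can be uncovered from the first week. The documents do not support that. They call the two devices identical apart from the battery and do not say that its absence is visible or can be felt. An active device is also spent after 5 days, so function would not separate the arms at return; only appearance, weight or opening the device could. This stands, and it limits the point to a risk.

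**Subjects are not told to expect pulsing.** Both scripts are conditional, and both arms receive needles, so local sensation is possible in either. In the group's previous trial, ear discomfort was reported by three active and three placebo subjects (Sections H and K). That is reassuring as far as it goes, but it rests on six reports of discomfort, not pulsing. The two scripts still disagree.

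**The plan does check blinding.** It does, through the subject guess. That detects and does not prevent, it comes after devices 1 to 3 have been handed back, and it leaves out placing doctors and coordinators.

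**If the discard instruction is the one followed, the staff route closes.** True. But Section I sets out weekly return and logging in detail, and Section F (Measurements and Data Collection) also records whether devices came back.

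**Fixed blocks of 10.** A reader might infer that 65% of assignments can be guessed and one in six known for certain. Those figures require every earlier arm to be known at once, which the plan's own return timing rules out for staff who rely on returned devices. Consent also precedes the breath and drink tests and the first placement, and no passage says that the same individuals recruit and place devices. Block prediction is secondary.

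**Conclusion.** The point holds as a risk to blinding. The plan has 3 of 4 used devices pass, unconcealed, to staff it says are blinded; contradicts itself on whether devices are returned at all; and gives two sensation scripts, one of which fits poorly with sub-threshold stimulation. Its only check comes after the fact. That matters because the primary outcome is self-reported.

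The size of any bias is unknown. Under the assumed inputs above, the false-positive rate would be 5.5% to 13%; with an intact blind it stays at 5%. Block prediction reaches at most about 65% correct guesses with full knowledge and no lag, and about 58% with the last two assignments unknown. Everything rests on whether the missing battery or an absent pulse can be noticed, which the documents leave open. This is a cheap improvement, not evidence that the double-blind claim is false.

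**What to change.** 1. **One return rule.** Reconcile Section F (treatment protocol and step 8 of EAD placement details) with Section I. The subject seals each used device in an opaque bag, which goes unopened to the existing unblinded coordinator, who logs and disposes of it. No placing doctor or blinded coordinator handles the used device.
2. **One sensation script.** Reconcile the two Section F passages into a single arm-neutral text read to every subject, consistent with whatever the protocol says about stimulation intensity.

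Optional and conditional:

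- Establish whether the missing battery can be seen or felt. If it can, have the manufacturer conceal it, for example with a dummy battery. This matters because the bag does not cover the placing doctor's handling of the new device, or the subject's own handling.
- Varying, undisclosed block sizes are a minor safeguard, relevant only if earlier arms are identified. They may leave a slight arm imbalance at the end.

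The cost is protocol wording, bags and a slightly longer path for logging returns. No extra subjects or staff are needed. A dummy battery, if needed, would be a small change to the manufacturer's order.
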